Study Protocol

Refinement of the *ECHT-intervention* against stigmatization of people with visible chronic skin diseases for further target groups

“Beruf und Gesundheit in körpernahen Dienstleastungen“ (BEGINN)

Principal investigator:

[name]. [name]

Co-investigators:

PD [name]
[name]

Sponsor:

Eucerin, Beiersdorf

Study coordination:

CVderm 
German Center for Health Services Research
in Dermatology

Institute for Health Services Research in Dermatology and Nursing (IVDP)
University Medical Center Hamburg-Eppendorf (UKE)
[name]
E-Mail: [contact]
[contact]

1. Synopsis

Short title	Destigmatization of skin diseases in the public
Sponsor	Beiersdorf / Eucerin Social Mission Programme
Collaborators	German Psoriasis Association (Deutscher Psoriasis Bund e.V., DPB)
Research objectives	The objective of this project is to adapt and test the “ECHT-intervention” for feasibility and effectiveness in professions dealing with health and body care (i.e. hairdressers, cosmetologists, nurses, and physiotherapists/occupational therapists).
Study design	A 3-hour-intervention including self-experience/exercises, education and a patient encounter will be developed in an interdisciplinary expert group with patient participation. The evaluation will follow a randomised controlled design against a control group receiving a non-stigma-related intervention. Eligible participants will be professionals from the following branches: hairdressers, cosmetologists, nurses, physiotherapists/occupational therapists. Feasibility and effectiveness with regard to primary (stigmatising attitudes) and secondary outcomes (satisfaction with the intervention) will be assessed at three time points: baseline/before the intervention, immediately after the intervention, 3-month follow-up.
Estimated number of participants	n = 120 (30 per profession)
Outcomes	The main outcome is stigmatising attitudes, which will be assessed by desire for social distance, agreement with skin disease-related misconceptions (e.g. psoriasis myths), agreement with skin disease-related stereotypes, (each adapted from Pearl et al. and reported and intended behaviour towards people with skin disease (Reported and Intended Behaviour Scale (RIBS); adapted from Evans-Lacko et al.). In addition, sociodemographic information, such as age and gender, will be recorded.
Data analysis	Effects will be analysed using mixed repeated-measures analysis of variance.
Benefits	The results of the program will provide new insights and markedly extended knowledge on measures to prevent/reduce stigmatization in visible chronic skin conditions. They will deliver unique data regarding the benefits of structured interventions against stigmatization. Future destigmatization programmes can be based on the outcomes of this project. Key results will be the first data on the effectiveness and benefits of an intervention against stigmatization in these important target groups. The new intervention is expected to be a path-breaking support in the psychosocial health prevention for people with skin diseases. It is in line with the WHO campaign for people-centered health care (PCHC) which is dedicated to improve the situation of people with chronic diseases worldwide [10]. Overall, the deliverable outcome will be an intervention format which can be used in many countries, increasing awareness and acceptance of skin diseases in the public. In total, the project completely fits the purpose and the vision of the Eucerin Social Mission and adds substantial value to the lives of people affected with skin diseases.

Timeline	Overall project duration is three years, including publication and dissemination. Initiation at any time starting with Q4/2021.
Ethics	The study will be carried out in compliance with the Helsinki Declaration and examined by the ethics committee of the University Medical Center Hamburg-Eppendorf.

2. Table of contents

1. Synopsis.....	2
2. Table of contents.....	4
3. Abbreviations.....	5
4. Responsibilities and addresses.....	6
4.1. Coordinating center.....	6
5. Background and objectives.....	7
5.1. Objectives.....	7
6. Study protocol	8
6.1. Study design and procedures	8
6.2. Participants	9
6.3. Outcomes	9
6.4. Data management and statistical analyses	11
6.5. Quality assurance.....	12
6.6. Data protection and ethics	12
7. Timelines and Milestones	13
8. References	15

3. Abbreviations

CVderm	German Center for Health Services Research in Dermatology
IVDP	Institute for Health Services Research in Dermatology and Nursing
T0	Baseline, immediately before the seminar
T1	Post-test, immediately after the seminar
T2	Follow-up, 3 months after the seminar
UKE	University Medical Center Hamburg-Eppendorf

4. Responsibilities and addresses

A first project to address these needs was a three-year funded project by the German Federal Ministry of Health (BMG; project number: ZMVI1-2517FSB809) 2018-2020 – the “ECHT-project”.⁶ Within this project, face-to-face interventions to reduce external stigmatization were developed in a multidisciplinary group and tested for effectiveness. The target groups were medical students and future educators and teachers. The interventions intended to sensitize them already during their studies or training to the risk of stigma related to visible skin diseases. The evaluation had a randomized controlled design. First analyses have shown that in both groups, medical students and future educators/teachers, the intervention significantly reduced the desire for social distance from people with psoriasis in the intervention group compared to the control group. In addition, the agreements to negative stereotypes and to disease-related false assumptions were significantly reduced in the intervention group but not in the control group. Based on these findings it is essential to further enlarge the target groups for such successful interventions against stigmatization. The vision is to create tools which permit prevention/reduction of stigmatization in a broad spectrum of society, thus adding value to the social mission. Important groups developing and promoting attitudes on stigmatization are professions in the health and body care sector. Some patients with visible skin diseases report feelings of rejection and stigma in such situations. For this, these professions have been chosen as targets of the planned intervention.

5.1. Objectives

This project aims to modify the “ECHT” intervention for health and body care professions and

evaluate its effectiveness. It was hypothesized that the intervention group would show a larger reduction in stigmatising attitudes towards people with visible chronic skin diseases compared to the control group.

6. Study protocol

6.1. Study design and procedures

Cross-sectional interventional study on health and body care professionals (i.e., hairdressers, cosmetologists, nurses, physiotherapists/occupational therapists) recruited in the area of Hamburg, Germany.

Participants will sign up for one of the seminar dates through the study website. Seminars will be randomly assigned to be intervention or control seminar.

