6.2. Participants

6.2.1. Number of participants

According to an a priori sample size calculation using G*Power¹¹ (F-tests for repeated measures ANOVA, within-between interaction) with the effect size obtained by Weinberger et al.¹⁰ (interaction effect for behavioural intentions: $\eta_p^2 = 0.02$), 82 participants are needed to obtain a power of 0.80 ($\alpha = 0.05$). To account for multiple testing and a potential drop-out rate of up to 20% at follow-up, we aim to include 120 participants in total.

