6.4.2. Statistical analysis

The statistical analyses will be conducted with the Statistical Package for the Social Sciences (SPSS v.27.0; IBM Corp., Armonk, NY). Descriptive statistics, i.e., absolute/relative frequencies and percentages for categorical variables and minimum, maximum, median, mean and standard-deviations for continuous variables, will be obtained for the total sample and subgroups of participants (e.g., by profession). The reliability of all questionnaires will be examined before conducting inference analyses, by calculating the Cronbach’s Alpha coefficients, considering $\alpha \geq 0.70$ as acceptable and $\alpha \geq 0.80$ as optimal.¹⁴ Assumptions of normality and sphericity will be checked by means of Shapiro-Wilk and Mauchly's Test of Sphericity, respectively.

Intervention effects on the primary outcomes will be analysed by means of 2 (Group: intervention, control) x 3 (Time: t0, t1, t2) repeated-measures analyses of variance (ANOVA). Subgroup analyses will be performed to assess potential differences between the professions. Intervention effects on the primary outcomes by profession will be analysed through 2 (Group: intervention, control) x 3 (Time: t0, t1, t2) x 3 (Profession: beauty, nurses, physical therapists) repeated-measures ANOVAs. The significance level will be established at a p-value ≤ 0.05 . Bonferroni correction for multiple testing will be applied. Effect sizes will be reported as η_p^2 , with $\eta_p^2 < 0.06$ indicating a small effect, $\eta_p^2 \geq 0.06$ indicating a medium effect and $\eta_p^2 \geq 0.14$ indicating a large effect.¹⁵ Post-hoc pairwise comparison will be used to further examine significant effects.

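### Whole seminars are randomised with no stated balance between arms or within professions, although a profession-by-group analysis is planned and the primary model omits profession

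*Protocol*

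**What the plan says.** The Synopsis calls the trial randomised: "The evaluation will follow a randomised controlled design against a control group receiving a non-stigma-related intervention". Its recruitment target is 120 people, 30 from each of four professions.

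Section 6.1 gives the whole allocation procedure in two sentences: "Participants will sign up for one of the seminar dates through the study website" and "Seminars will be randomly assigned to be intervention or control seminar". The unit of allocation is therefore the seminar, and participants choose their seminar themselves. The protocol does not state the number or size of seminars, the allocation ratio, any blocking or stratification, or whether a seminar is open to one profession or to all.

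Section 6.2.1 sizes the trial on "F-tests for repeated measures ANOVA, within-between interaction", using an effect taken from the "interaction effect for behavioural intentions" in an earlier trial, and concludes that "82 participants are needed to obtain a power of 0.80". The target is then raised to 120, partly to allow for dropout of up to 20%.

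Section 6.4.2 analyses the primary outcomes by a Group × Time repeated-measures ANOVA. It adds: "Subgroup analyses will be performed to assess potential differences between the professions". This is to be done by a Group × Time × Profession ANOVA with three profession levels: the beauty trades, nursing and physical therapy.

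**The concern.** When whole seminars are allocated, the number of randomised units is the number of seminars, not 120. Unless the scheme forces balance, a modest number of units can divide unevenly. Arm sizes then depart from the equal groups behind the sample size.

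The profession analysis is more exposed. It needs intervention and control participants at every profession level. If seminars are run by profession, all of one profession's seminars could fall in the same arm. That level would then have no intervention contrast, and no analysis could recover it after the seminars had been held. A less extreme imbalance would partly confound profession with arm in the primary comparison, where profession is not in the model.

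**Working it through.** **1. Reproducing the planned sample size.** From section 6.2.1: partial eta squared 0.02, alpha 0.05, power 0.80. From section 6.4.2: k = 2 groups, m = 3 times. Assumed, because not stated: correlation between times ρ = 0.5, sphericity (epsilon = 1), equal groups.

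- f² = 0.02/0.98 = 0.0204
- λ = f²·N·m/(1 − ρ), with df1 = (k − 1)(m − 1) = 2 and df2 = (N − k)(m − 1)
- N = 82: λ = 0.0204 × 82 × 3/0.5 = 10.04, df2 = 160, power 0.809. N = 80 gives 0.799.

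The stated 82 is reproduced for equal groups. Allowing for dropout, 82/0.8 = 102.5, so 103 would be enough. The planned 120 leaves 120 × 0.8 = 96 completers.

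**2. Power when the arms are unequal.** With a fraction p of participants in one arm, f² is multiplied by 4p(1 − p). At N = 96, alpha 0.05, clustering by seminar ignored:

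| Split | 4p(1 − p) | Power |
|---|---|---|
| 1:1 | 1.000 | 0.871 |
| 2:1 | 0.889 | 0.827 |
| 3:1 | 0.750 | 0.754 |

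**3. How likely such splits are.** Assumed: simple randomisation of K equal-sized seminars, so the number in one arm is Binomial(K, 1/2). For K = 8, a split of 2:1 or worse means 6:2 or beyond: 2 × (28 + 8 + 1)/2⁸ = 74/256 = 0.29.

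| K | 2:1 or worse | 3:1 or worse |
|---|---|---|
| 8 | 0.29 | 0.29 |
| 10 | 0.34 | 0.11 |
| 12 | 0.39 | 0.15 |
| 16 | 0.21 | 0.08 |

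The two columns agree at K = 8 because 5:3 is milder than 2:1 and the next step, 6:2, is already 3:1.

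**4. A profession level without one arm, if seminars are profession-specific.** With s seminars per profession under simple randomisation, nursing or physical therapy lacks an arm with probability q = 2 × 0.5^s. The beauty level is taken to pool hairdressers and cosmetologists. It then has 2s seminars and lacks an arm with probability b = 2 × 0.5^(2s). At least one of the three levels lacks an arm with probability 1 − (1 − b)(1 − q)²:

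- s = 2: 1 − 0.875 × 0.5² = 0.78
- s = 3: 1 − 0.96875 × 0.75² = 0.46
- s = 4: 1 − 0.9922 × 0.875² = 0.24

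Blocking on arm totals alone, without strata, does not remove this. By enumeration the probabilities become 0.66, 0.32 and 0.14.

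**5. The same risk if professions mix freely.** Thirty people per profession were spread at random over K seminars (100,000 simulated trials per K). The chance that any of the four professions lacks an arm is 0.035, 0.012, 0.005 and 0.003 for K = 6, 8, 10 and 12.

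**The case against.** The strongest reply is that the protocol is silent rather than wrong. It says seminars are assigned at random, which does not exclude blocks or strata, and these may be set out in a randomisation plan that is not shown. This stands against one tempting reading, that the trial uses simple randomisation over a handful of seminars. Neither the method nor the number is stated. The reply does not remove the point: the allocation rule belongs in the design section, and the one given there does not support the profession analysis planned in the same document.

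Second, nothing says that seminars are profession-specific. Section 6.1 describes one sign-up route, and sections 6.1.1 and 6.1.2 describe one intervention seminar and one control seminar without versions by profession. This also stands: a reader might infer that a profession is likely to lack an arm, but with free mixing that is rare. Self-chosen dates do not guarantee free mixing, though, since colleagues may book together.

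Third, a reader might count four professions and obtain 1 − (1 − q)⁴ = 0.94, 0.68 and 0.41 for 2, 3 and 4 seminars each. The planned ANOVA has three levels, so those figures overstate the risk to it.

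Fourth, the cost to the primary test is modest. At alpha 0.05 a 2:1 split keeps power above 0.80. If the Bonferroni correction runs over the four primary outcomes (alpha 0.0125, an assumption), power is 0.72 at 1:1 and 0.66 at 2:1. Most of that shortfall comes from multiplicity, not imbalance.

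Fifth, stable differences between professions cancel out of within-person change. Imbalance biases the Group × Time test only if professions differ in how they change. This is right, and it is why the adjustment must include the interaction of profession with time.

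**Conclusion.** The point holds as a conditional weakness of the design. Section 6.1 secures neither balanced arms nor both arms within each profession level, section 6.4.2 needs the latter, and the primary model does not adjust for profession.

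The effect on the primary test is limited. Under simple randomisation of 8 to 16 equal-sized seminars, a 2:1 or worse split has probability about 0.2 to 0.4. Power falls from about 0.87 to 0.83 at 2:1, and to about 0.75 only at 3:1. These powers assume ρ = 0.5, alpha 0.05 and 96 completers. They also ignore clustering by seminar, which would lower them all.

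The effect on the profession analysis depends on a fact the protocol does not give. The chance of a level without one arm is about 0.78, 0.46 or 0.24 if seminars are profession-specific, and about 3.5% or less if they mix. The documents do not support saying that the arms will be badly unequal or that a profession contrast will be lost. They do leave open a loss that cannot be repaired later and is cheap to prevent.

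**What to change.** In section 6.1, state the planned number of seminars and whether each is for one profession or mixed. Assign seminars 1:1 in blocks or matched pairs, stratified by profession where they are profession-specific, with at least one seminar per arm for each analysed profession level. This needs at least two seminars per level; with only one, no scheme helps. With at least two profession-specific seminars per profession and balanced stratified assignment, the chance of a level lacking an arm is zero. Arms are then about 60:60, or 48:48 after 20% dropout.

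In section 6.4.2, add profession and its interaction with time to the primary repeated-measures model.

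The cost is small. Dates must be listed in pairs before assignment. A three-level profession factor takes 2 between-person degrees of freedom, and its interaction with time takes 2 × 2 = 4. At 96 completers the within-person error degrees of freedom go from (96 − 2) × 2 = 188 to 184.

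### Seminars are randomised, but the sample size and the ANOVAs treat participants as independent; if change over time correlates within seminars, the planned test is anti-conservative and power is overstated

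*Protocol*

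**What the plan says.** Section 6.1 describes a two-step allocation. Participants choose a date ("Participants will sign up for one of the seminar dates through the study website"), and the dates are then allocated ("Seminars will be randomly assigned to be intervention or control seminar"). No randomisation of individuals is described anywhere.

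Section 6.2.1 sizes the trial in G*Power with the option "F-tests for repeated measures ANOVA, within-between interaction" and concludes that "82 participants are needed to obtain a power of 0.80". The increase to 120 is attributed to multiple testing and to "a potential drop-out rate of up to 20% at follow-up, we aim to include 120 participants in total". Clustering is not mentioned.

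Section 6.4.2 fixes the analysis: "Intervention effects on the primary outcomes will be analysed by means of 2 (Group: intervention, control) x 3 (Time: t0, t1, t2) repeated-measures analyses". A second ANOVA adds profession as a three-level factor. Neither contains a seminar term.

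**The concern.** When groups are randomised, the treatment comparison is a comparison of groups. The planned ANOVA judges the group-by-time effect against variation between participants, with 2(N − 2) error degrees of freedom. If participants in the same seminar change in a similar way, that error term is too small and the degrees of freedom are too many.

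Such correlation is plausible here. Under 6.1.1, everyone in an intervention seminar hears the same person with psoriasis for 60 minutes and hears that person's answers to the group's questions. This falls between T0 and T1, so it acts on change, which is what the group-by-time test measures.

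At stake is the main hypothesis on all four primary outcomes. A significant result could reflect a few unusually good or poor seminars, and the effective sample size would be below the headcount. The profession ANOVA has the same weakness.

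**Working it through.** **1. The plan's own figure.** From 6.2.1: partial eta squared 0.02, alpha 0.05, power 0.80. From 6.4.2: k = 2 groups, m = 3 times. Assumed because not stated: the G*Power defaults of correlation rho = 0.5 and epsilon = 1.

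- f² = 0.02/0.98 = 0.0204
- Non-centrality lambda = f² × N × m/(1 − rho) = 0.0204 × N × 6
- df1 = (k − 1)(m − 1) = 2; df2 = (N − k)(m − 1) = 2(N − 2)
- N = 80: lambda = 9.80, power 0.799
- N = 82: lambda = 10.04, power 0.809

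The stated 82 is reproduced exactly with no cluster term, so it rests on independent participants.

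**2. Power with clustering.** 120 enrolled less 20% leaves 96 completers. Design effect DEFF = 1 + (c − 1) × ICC, with c completers per seminar; lambda is divided by DEFF. Both c and ICC are assumptions. Alpha is 0.05.

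| c | ICC | DEFF | 96/DEFF | lambda | Power |
|---|---|---|---|---|---|
| any | 0 | 1.00 | 96 | 11.76 | 0.87 |
| 8 | 0.02 | 1.14 | 84 | 10.31 | 0.82 |
| 8 | 0.05 | 1.35 | 71 | 8.71 | 0.75 |
| 10 | 0.05 | 1.45 | 66 | 8.11 | 0.72 |
| 15 | 0.10 | 2.40 | 40 | 4.90 | 0.49 |

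These rows keep df2 = 2(N − 2). A valid test has degrees of freedom tied to the number of seminars, so in that respect they are optimistic. They also assume that seminar effects inflate all time contrasts equally. If effects arise only after the seminar, the loss at a given ICC is smaller.

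**3. Type I error of the planned 2 × 3 ANOVA.** Simulated under no treatment effect, with at least 4,000 runs per scenario, 12 seminars of 10 and nominal 5%. Here ICC is the seminar variance at a time point divided by that variance plus the within-person residual variance.

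| Seminar effects | ICC 0.02 | ICC 0.05 | ICC 0.10 |
|---|---|---|---|
| Stable shift, same at T0, T1, T2 | 5% | 5% | 5% |
| T1 and T2 only, persistent, intervention arm only | 5–6% | 6% | 7–8% |
| T1 and T2 only, independent, intervention arm only | 6% | 7–8% | 10% |
| T1 and T2 only, both arms (persistent to independent) | 6–7% | 8–10% | 10–16% |
| Independent at T0, T1 and T2, both arms | 8% | 13% | 21% |

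At ICC 0 the test holds its level (about 5%), so the excess comes from clustering. T0 is taken immediately before the seminar (6.3), so a seminar's content cannot correlate T0 scores. The last row is therefore an upper case. Seminar size matters too: under that last structure, 20 seminars of 6 give 7%, 9% and 14%, and 8 seminars of 15 give 10%, 18% and 29%.

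**The case against.** **A stable seminar effect is harmless.** Differences between seminars that come only from who signs up for which date cancel in the group-by-time interaction. This stands: inflation needs correlated change, and the documents give no ICC to show how much there is.

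**The increase to 120 may absorb the loss.** In part it does. With 96 completers, 8 per seminar and ICC 0.02, power is still 0.82 at alpha 0.05. But 6.2.1 has already assigned that increase to multiplicity and drop-out, and extra participants do not correct the type I error. Separately, if Bonferroni is taken over the four primary outcomes (alpha 0.0125, an assumption), power is already 0.72 before any clustering. That part of a shortfall is a multiplicity matter.

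**The mechanism is weaker in the control arm.** This stands. Its matching 60 minutes is an e-learning tool (6.1.2), so the patient encounter is shared in the intervention arm only. A reader might also assume a common facilitator, but neither seminar description mentions one. This is why the intervention-only rows are shown.

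**The synopsis speaks of a mixed analysis, and an SAP may exist.** In the synopsis the word most naturally describes an ANOVA with between- and within-person factors; no seminar effect is named. An SAP could add one, but 6.4.2 does not leave the model open, and 6.2.1 has fixed the sample size under independence.

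**Conclusion.** The mismatch between the unit of randomisation and the unit of sizing and analysis is explicit, and nothing in the protocol repairs it. The direction of both consequences holds for any positive within-seminar correlation of change; the size is conditional on figures that the protocol does not give. On the most relevant structure, with effects arising after the seminar, 12 seminars of 10 give a true level of roughly 6–16% over ICC 0.02 to 0.10 if both arms are affected. If only the intervention arm is affected, it is roughly 5–10%.

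A reader might infer that the p-values are bound to be too small, or that 80% power cannot be reached. The documents support neither as a certainty: a purely stable seminar shift leaves the level at 5%, and small seminars with a low ICC keep power above 0.80 at alpha 0.05. The supported conclusion is that the plan leaves error control and power dependent on an unstated correlation that its own intervention makes likely.

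**What to change.** - **6.1:** call the design cluster-randomised, and state that the seminar identifier is kept in the analysis dataset.
- **6.4.2:** replace both ANOVAs by a linear mixed model with random effects for participant and for seminar, including seminar-by-time, and small-sample degrees of freedom (Satterthwaite or Kenward-Roger). SPSS MIXED can serve. If there are few seminars, for example four per arm, these variance components may be poorly estimated, and a seminar-level analysis of mean change is the simpler choice.
- **6.2.1:** state the expected number and size of seminars, and restate the power of the planned 120 by dividing the analysed number by 1 + (c − 1) × ICC over a stated range, for example ICC 0.01 to 0.10. This does not require more enrolment; it requires that the power be reported as it is.

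The cost is protocol wording and a different procedure, with no additional measurements. The downside is wider confidence intervals and a less favourable power statement.
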